5.1.3.1 Prior therapies date imputation

Same as for medications above.

5.1.3.2 Post therapies date imputation

Same as for medications above.

5.1.3.3 Other imputations

Non-response imputation

NRI assumes that a participant is a non-responder if there are no valid immune response assessments after receiving both doses of the vaccine. Hence, for missing data the primary endpoint of achieving immune response as defined by a positive SARS-CoV-2 qualitative IgG antibody assay ≥ 14 days after full course (2 doses) vaccination (yes/no) will be imputed as “No”.

MS relapse date imputation

The following algorithm will be used to estimate relapse start dates for which only partial information is known. Note that “index date” refers to the date of Visit 1 (Screening).

Missing day only:

- The first day of the month will be assigned to the missing day. In case the relapse start date occurs in the same month as the index date, the relapse start date will be imputed as the index date.

The following algorithm will be used to estimate relapse stop dates for which only partial information is known.

Missing day only:

- The last day of the month will be assigned to the missing day or truncated to have a maximum duration of 90 days.

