2.1.1 General definitions

Treatment of interest

The treatment of interest will refer to the administration of a COVID-19 mRNA vaccine (either Pfizer or Moderna) to participants in each of the 6 cohorts. Participants will obtain a COVID-19 mRNA vaccine from their HCP (private insurance) or appropriate federal, state or local program.

Additional treatment

- Ofatumumab provided by Novartis in an auto-injector containing 20 mg s.c. ofatumumab (20 mg/0.4ml) for s.c. administration to participants in **Cohort 1** as per the assessment schedule.
- Commercially prescribed ofatumumab treatment for participants in **Cohort 2** as per their current dosing schedule.

- Commercially prescribed interferon or glatiramer acetate treatment for participants in **Cohort 3** as per their current dosing schedule.
- Commercially prescribed ofatumumab treatment for participants in **Cohort 4** as per their current dosing schedule.
- Commercially prescribed interferon or glatiramer acetate treatment for participants in **Cohort 5** as per their current dosing schedule.
- Commercially prescribed ofatumumab treatment for participants in **Cohort 6** as per their current dosing schedule

Study day, onset day, and event duration

The **study day** of an assessment will be derived relative to the date of Visit 2 (Study Day 1), primarily for use in the derivation of analysis visits using visit windows (see [Section 2.4.1.1](#)).

For data including but not limited to adverse events, medications, medical history, non-drug therapies/procedures and MS relapses, the **onset day** will be derived relative to the date of Visit 1 (Screening) as described below.

For event dates on or after the date of Visit 1, the day of the event will be calculated as follows:

- (date of event – date of Visit 1) + 1

For event dates prior to the date of Visit 1, the day of the event will be calculated as follows:

- (date of event – date of Visit 1)

The **duration of an event** in days will be calculated as follows:

- (event end date – event start date) + 1

Screening

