2.3.3 MS history

The number and percentage of participants with a relapse in the last 90 days prior to screening will be presented by cohort group.

The following variable will be summarized descriptively as a continuous variable by cohort group:

- Time (days) from onset of most recent relapse (in the last 90 days prior to screening) to Visit 1 (Screening), in participants with a relapse in the last 90 days prior to screening

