2.7.4 Other safety data

2.7.4.1 MS relapse

The number and percentage of participants with 0, 1, 2 or ≥ 3 confirmed relapses during the study will be presented by cohort group. In addition, the number and percentage of participants with at least 1 confirmed relapse during the study will be presented by cohort group.

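### SAP 5.1.3.3 uses one missing-day rule for history and on-study relapses, so a partly dated pre-study relapse can be moved onto Visit 1 or out of the 90-day look-back

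*SAP*

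**What the plan says.** SAP 5.1.3.3 gives the general rule for a relapse start with a missing day: "The first day of the month will be assigned to the missing day". The exception is the month of the index date: "In case the relapse start date occurs in the same month as the index date, the relapse start date will be imputed". The value used in that case is the index date itself. The section defines the index date as Visit 1 (Screening). It says nothing about whether the relapse was reported as history or as a new event.

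Two outputs can draw on these dates:

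- SAP 2.3.3 tabulates "The number and percentage of participants with a relapse in the last 90 days prior to screening", and summarises the days from the most recent such relapse to Visit 1.
- SAP 2.7.4.1 tabulates participants by number of "confirmed relapses during the study will be presented by cohort group". It gives no date at which that period begins for relapses.

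SAP 2.1.1 lists MS relapses among the data whose onset day is counted from Visit 1. An event dated on Visit 1 falls on the later side of that boundary and gets Day 1.

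**The concern.** One rule serves two populations of relapses that sit on opposite sides of the index date. For a relapse first reported after Visit 1, setting a missing day in the Visit 1 month to Visit 1 is reasonable, since the relapse cannot have started sooner. For a relapse reported at screening as history, the same step moves it to the first date that is no longer before screening. In earlier months the first-of-month step moves dates backwards, and in the month that contains day -90 it can carry a relapse out of the look-back.

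What is at stake is the baseline percentage with a recent relapse, the time since that relapse and, depending on how the on-study period is read, the on-study relapse count. Each cohort group is planned at 22 participants (SAP 3), so one misfiled participant moves a percentage by 1/22 = 4.5 points.

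**Working it through.** The documents give no relapse count and no number of partial dates, so there is no figure of the plan's own to reproduce. The check applies the rule as written.

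**Single records**

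- Visit 1 on 15 October 2021, so day -90 is 17 July. A relapse that truly began on 1 to 14 October, day missing, is dated 15 October: 0 days since relapse, onset Day 1. A relapse that truly began on 17 to 31 July is dated 1 July, which is 106 days before Visit 1.
- Visit 1 on 20 April 2021. A relapse on 28 January is 82 days back and inside the look-back. It is dated 1 January, which is 109 days back.

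**Average share**

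Assumptions: Visit 1 is uniform over the calendar; true onset is uniform over the 90 days before Visit 1; the day is missing; both tables use the imputed date.

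- Look-back days in the month of Visit 1: if Visit 1 falls on day d of its month, there are d - 1 such days. Summed over a month of length L this is L(L - 1)/2, which is 465 for 31 days, 435 for 30 and 378 for 28. Over a year: (7 × 465 + 4 × 435 + 378)/365 = 5373/365 = 14.72 days. As a share: 14.72/90 = 16.4%.
- Look-back days in the oldest month that are dated beyond day -90: if day -90 falls on day d of a month of length L, there are L - d + 1 such days, or none when d = 1. The sum over the month is again L(L - 1)/2, so the mean is again 14.72 days, or 16.4%.
- Remainder: (90 - 2 × 14.72)/90 = 67.3% stay inside the look-back. Their time since relapse is overstated by 14.7 days on average, which is the ordinary cost of a first-of-month convention and is not counted here as misfiling.

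Applying the rule to every Visit 1 date from 1 April 2021 to 31 March 2022 and to each of the 90 onset days (365 × 90 = 32,850 pairs) gives 5,373 moved onto Visit 1 (16.4%), 5,373 moved beyond 90 days (16.4%) and 22,104 kept (67.3%). Visit 1 dates across 2021 to 2024 give the same shares to within 0.1 point. Each shift covers between 0 and 30 days, depending on the Visit 1 date.

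**Direction**

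Across the same dates, no relapse from 91 to 130 days back is pulled into the look-back, and no true on-study relapse is dated before Visit 1. The errors do not offset each other.

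**Comparison with the neighbouring rules**

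The AE and medication rules (SAP 5.1.2 and 5.1.3) also use the index date in the index month. In earlier months, however, they use the last day of the month. They also reset an imputed start that falls after a complete stop date; the relapse rule has no such reset. With Visit 1 on 15 October, a relapse with a missing start day and a complete stop date of 12 October would start on 15 October. The duration formula in SAP 2.1.1 (end minus start, plus 1) then gives 12 - 15 + 1 = -2 days.

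**The case against.** Several points on the other side are sound.

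- **Nothing happens without partial dates.** If every relapse start is complete, the rule is never used. The documents do not show that a single record is affected.
- **Entry into the on-study table is an inference.** A reader might conclude that a relapse moved onto Visit 1 will be counted in SAP 2.7.4.1. That section sets no start date and counts only confirmed relapses. The rule that on-study means on or after Visit 1 is stated for AEs (SAP 2.7.1), and SAP 2.1.1 only numbers days. The protocol's assessment schedules collect MS relapse at screening and at later visits, so allocation by collection visit fits the text equally well.
- **Loss from the look-back is also conditional.** The 90-day percentage may come from a direct site report. It would then stand, and only the time since relapse would be wrong.
- **The uniform assumption probably overstates the Visit 1-month share.** Those relapses lie at most 30 days before Visit 1. Protocol 5.2 excludes systemic corticosteroids within 30 days before screening, and Protocol 6.2.3 makes a short corticosteroid course the standard where a relapse needs treatment. Untreated relapses remain possible, so the share is reduced but not removed.
- **Forcing every history relapse into the look-back would create the opposite error.** On average half the days of the oldest, partly covered month lie outside the 90 days, and the present rule excludes those correctly.

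These points limit the claim but do not remove it. Whichever source the tables use, an affected record gets either the wrong category or an implausible value: 0 days for a relapse that preceded screening, or more than 90 days in a table restricted to 90.

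**Conclusion.** The rule as written gives wrong results for two kinds of history relapse with a missing start day: those in the month of Visit 1, and those inside the look-back but in its oldest month. Under uniform dates and tables built on imputed dates, each kind makes up about 16% of missing-day look-back relapses. About a third (2 × 5,373/32,850 = 32.7%) would then leave the history table. The Visit 1-month part is probably smaller because of the steroid criterion.

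A reader might infer that both relapse tables are in fact miscounted. The documents do not support that: the number of partial dates is unknown, the source of the 90-day percentage is not stated, and the on-study period is undefined for relapses. Nor do they show that the rule came in shortly before database lock; the SAP's update log says only that the update was made before lock.

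The consequence is minor. Relapse is neither an objective nor an endpoint, both tables are descriptive, no hypothesis test is planned, and the immune-response analyses are untouched. The correction is still worth making because it is specific and nearly free.

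**What to change.** In SAP 5.1.3.3, classify each relapse as history or on-study by where it was reported, before any date is imputed. Then:

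1. For history relapses, bound the imputed start to no later than Visit 1 minus 1 day and no later than any complete stop date. Never count them in SAP 2.7.4.1.
2. Where the site reported the relapse as within the last 90 days, also bound the start to no earlier than Visit 1 minus 90 days. Where there is no such report and the recorded month straddles day -90, do not force the relapse into the look-back; list it as undetermined.
3. Keep the index-date rule only for relapses reported as new since Visit 1.
4. Define the on-study period in SAP 2.7.4.1 to match, and state in SAP 2.3.3 whether the percentage rests on the site's report or on the imputed date.

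Which date is chosen inside the bounds is a matter of preference; the midpoint is one option.

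The cost is a few sentences in the SAP and a small programming change. No new data are needed, provided the database keeps the visit at which each relapse was reported.

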5.2 AEs coding/grading

Adverse events will be coded using the MedDRA terminology. The MedDRA version used for reporting the study will be indicated in a footnote on relevant outputs.

5.3 Laboratory parameters derivations

There are no laboratory parameter derivations for this study.

5.4 Statistical models

5.4.1 Analysis supporting primary objective(s)

There is no hypothesis testing planned for the analysis supporting the primary objective of this study.

5.4.2 Analysis supporting secondary objective(s)

There is no hypothesis testing planned for the analyses supporting the secondary objectives of this study.

